24%	326	260	212	178	152	130	114
26%	436	336	268	218	182	154	134
28%	612	448	344	274	224	186	158

3.8d: Data analysis for Aims 2 and 3 (Hypothesis 2: ABC-I and CBT-I will be similarly effective in improving self-reported and objectively measured sleep from baseline to post-treatment; Hypothesis 3: ABC-I and CBT-I will be similarly effective in improving self-reported and objectively measured sleep from baseline to 3-months follow-up).

Two Step Hypothesis Testing of Non-inferiority: Hypotheses 2 and 3 seek to show that ABC-I is not inferior to CBT-I in terms of treatment effects (i.e., changes in sleep quality). Non-inferiority is established by framing the null

hypotheses in terms of the difference between the treatment means and comparing this difference to a pre-specified value, delta (δ), which represents the equivalence margin.

Determination of delta (δ): We elected to use a value of δ equivalent to an effect size of $d=0.40$. (i.e., 4/10ths SD). With respect to ISI, this represents a 2 point difference between the treatment effects. For PSQI, this represents a 1.4 point difference, and for actigraphically-estimated sleep percent, a difference of 5%.

Description of analysis: With respect to this study, non-inferiority is established by showing that the efficacy of ABC-I is no more than δ units less than CBT-I (**Table 12**).⁸⁸ This is tested by formulating a one sided null hypothesis that the difference between CBT-I and ABC-I is greater than or equal to δ (i.e., $H_0: \mu_{CBT-I} - \mu_{ABC-I} \geq \delta$) against the alternative hypothesis that the difference is less than δ (i.e., $H_A: \mu_{CBT-I} - \mu_{ABC-I} < \delta$). If the null

[figure not shown]
Table 12: Hypothesis testing in a non-inferiority study comparing ABC-I to CBT-I.

Type of study	Hypotheses	
	Null hypothesis (H_0)	Research Hypothesis (H_1)
Traditional comparative study	There is no difference between ABC-I and CBT-I	There is a difference between ABC-I and CBT-I
Non-inferiority study	ABC-I is inferior to CBT-I	ABC-I is not inferior to CBT-I (H₂ and H₃)

hypothesis is rejected, then the non-inferiority of ABC-I is established. For Aims 2 and 3, this two step process avoids the pitfall of erroneously interpreting a failure to reject the null hypothesis as evidence of no difference

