between the treatment groups. **Figure 8** illustrates four hypothetical patterns of results with respect to the outcome ISI using $\delta = 2$. In **Result 1**, the mean of CBT-I is greater than ABC-I and the confidence interval of this difference includes δ , and the noninferiority of ABC-I is not established. In **Result 2**, the mean of CBT-I is greater than ABC-I, however, the confidence interval excludes δ and the noninferiority of ABC-I is established. **Result 3** shows that the mean of ABC-I is greater than CBT-I and the confidence interval excludes δ , establishing the non-inferiority of CBT-I. **Result 4** shows that the mean of ABC-I is greater than the mean of CBT-I, however, the confidence interval includes δ so the noninferiority of ABC-I is not established.

Figure 8: Depiction of possible results for non-inferiority testing of ABC-I compared to CBT-I. The figure shows mean differences and 95% CI.

Statistical Analysis: To conduct the non-inferiority tests of Hypotheses 2 and 3, we will first use a 2 (group) by 3 (time) mixed model analysis of variance (ANOVA). The ABC-I vs. CBT-I groups will form the 2-level between groups factor, and the 3 time points (baseline, post-treatment, follow-up) will form the within groups factor. The null hypothesis will be that the differences between groups are greater than or equal to delta, as specified above, for ISI (2 points), PSQI (1.8 points) and sleep percent (5%).

Hypothesis 2 will compare the impact of the ABC-I to CBT-I at post-treatment (as compared to baseline) in terms of self-reported (ISI total score and PSQI total score) and objectively-measured (actigraphically-measured nighttime percent sleep) sleep quality variables. For each outcome measure, a 2 (group) by 3 (time) mixed model analysis of variance (ANOVA) will be performed. To directly test the impact of ABC-I vs. CBT-I on the change in outcomes from baseline to post-treatment, a planned interaction comparison will be tested that crosses treatment group (ABC-I vs. CBT-I) with time using a 1-1-0 contrast for the time factor). This interaction comparison will be used to directly test this hypothesis, that the ABC-I group shows greater positive changes (from baseline to post-treatment) on the outcome measures as compared to the CBT-I group.

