Hypothesis 3 will explore whether improvements seen at post-treatment are maintained over a 3-month follow-up time period. As with hypothesis 2, for each outcome measure, a 2 (group) by 3 (time) between/within analysis of variance (ANOVA) will be performed, but two interaction contrasts will be examined. The primary contrast of interest will examine impact of ABC-I (compared to CBT-I) on the change from baseline to 3 month follow-up by applying a -1 0 1 contrast to time and interacting that with treatment group. This interaction contrast will assess the impact of the ABC-I (compared to CBT-I) from baseline to the 3 month follow-up, assessing the persistence of the treatment effects. A secondary contrast will examine the change from post-treatment to six month follow-up by applying a 0 -1 1 contrast on time and interacting that with treatment group. This secondary comparison will assess differences in changes from post-treatment to 3 month follow-up for the ABC-I and CBT-I groups. Conceptually, this second contract will test whether there is either continued improvement after post-treatment (i.e., sleep is better at 3 months follow-up compared to post-treatment, or whether there is relapse (i.e., sleep is worse at 3 months follow-up compared to post-treatment).

Sample Size Calculations: For Aims 2 and 3, the required sample size was determined based on the minimum clinically-meaningful difference between the two treatments, rather than on the estimated effect size for an active treatment versus control condition. This non-traditional approach is required for comparative effectiveness designs.⁸⁸ To develop estimates of clinically-meaningful differences between treatments, we examined studies of CBT-I in the published literature.⁸⁹⁻⁹¹ We then considered clinically meaningful changes in ISI and PSQI scores and in objectively-measured sleep percent. We determined that a difference between the two treatment groups of more than 2 points on the ISI or PSQI, or more than 5% in objectively-measured sleep percent would constitute a clinically-meaningful difference between the treatments. This represents an effect size of approximately $d=0.40$ (that is, 4/10s of a standard deviation for each outcome measure). The required sample size (with alpha=.05 and .80 power) to detect for an effect size of 0.40 is n=138. We plan to randomize

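### The Figure 8 guide to reading the non-inferiority interval does not fit the one-sided hypothesis in Section 3.8d: Result 3 credits the wrong arm, the side of the margin and the scale are unstated, and the 95% interval is not reconciled with alpha .05

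*Combined protocol and SAP*

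**What the plan says.** Section 3.8d (Description of analysis) defines non-inferiority as showing that "the efficacy of ABC-I is no more than δ units less than CBT-I". The test is a "one sided null hypothesis that the difference between CBT-I and ABC-I is greater than or equal to δ", and its rejection establishes the non-inferiority of ABC-I. Table 12 lists no hypothesis about non-inferiority of CBT-I.

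The text then describes four hypothetical patterns in Figure 8, for the ISI with δ = 2:

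- **Result 1:** CBT-I greater, interval includes δ. ABC-I not established.
- **Result 2:** CBT-I greater, interval excludes δ. ABC-I established.
- **Result 3:** ABC-I greater, interval excludes δ, "establishing the non-inferiority of CBT-I".
- **Result 4:** ABC-I greater, interval includes δ, "so the noninferiority of ABC-I is not established".

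The caption adds: "The figure shows mean differences and 95% CI". The Sample Size Calculations paragraph for Aims 2 and 3 reads "The required sample size (with alpha=.05 and .80 power", followed by an effect size of 0.40 and n=138. It does not say whether that alpha is one-sided or two-sided.

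**The concern.** The four patterns are the plan's only worked illustration of how to turn a confidence interval into a conclusion for Aims 2 and 3. Two of them concern a point estimate on the ABC-I side, and their verdicts do not both follow from the null hypothesis they are meant to illustrate. A decision guide that conflicts with its own hypothesis leaves room to choose between rules after the data are seen.

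Three things a reader needs are not stated: the side on which δ lies in Results 3 and 4, whether *greater* refers to improvement or to the raw ISI total (Section 3.5d scores the ISI so that higher is worse), and whether the test is at one-sided .05 or .025. The last of these changes the chance that the trial succeeds.

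**Working it through.** **Inputs**

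- ISI margin of 2 points, set equal to d = 0.40 (3.8d, Determination of delta). Implied SD = 2/0.40 = 5.0.
- 148 randomized, 74 per arm (3.8c, Sample Size Calculations).
- alpha .05, power .80, n = 138 (3.8d, Sample Size Calculations).
- 95% interval (Figure 8 caption).
- Assumed: normal theory, data on all 148, a true difference of zero for power, and SD 5 for the quantity compared. The documents do not say whether that SD is of a score or of a change.

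**The plan's own figure**

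n per arm = 2(z₁₋α + z₀.₈₀)²/d².

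- One-sided .05: 2(1.645 + 0.842)²/0.16 = 77.3, so 78 per arm, 156 in total.
- One-sided .025: 2(1.960 + 0.842)²/0.16 = 98.1, so 99 per arm, 198 in total.

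Neither gives 138. One-sided .05 reaches 69 per arm at d = (1.645 + 0.842)√(2/69) = 0.423, and the paragraph does call 0.40 approximate. This mismatch is a separate matter and does not affect the logic below.

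**The patterns against the null**

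Let D = CBT-I minus ABC-I in improvement. The null is D ≥ +2. It is rejected, and ABC-I is non-inferior, exactly when the upper confidence limit is below +2.

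| Pattern | Plan's verdict | If δ is +2 | If δ is -2 |
|---|---|---|---|
| Result 3: D < 0, δ excluded | CBT-I non-inferior | Upper limit is below +2, so the null is rejected. ABC-I should be credited; the wrong arm is named. | With the interval above -2, true of CBT-I but not a trial hypothesis. ABC-I is also non-inferior and this is omitted. |
| Result 4: D < 0, δ included | ABC-I not established | Upper limit is at or above +2, so the null stands. The verdict is correct. | Wrong whenever the upper limit is below +2. |

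The last cell for Result 3 follows because a symmetric interval centred below 0 with a lower limit above -2 must have an upper limit below +2. So +2 leaves Result 3 wrong, and -2 leaves Result 3 off the hypothesis and Result 4 generally wrong. No single placement makes both fit.

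Results 1 and 2 fit the null with δ at +2, with one gap: an interval wholly above +2 also excludes δ, and Result 2 read literally would then credit ABC-I.

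**The scale**

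The word efficacy in 3.8d supports the improvement scale used above. On raw ISI, ABC-I is doing worse in Results 3 and 4. With the margin on the side where ABC-I is worse, Result 4 is correct and Result 3 should still credit ABC-I. Result 1 then becomes doubtful, because CBT-I is the worse arm yet ABC-I is refused.

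**Can Result 4 occur against +2?**

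- SE = 5√(2/74) = 0.822; 95% half-width = 1.96 × 0.822 = 1.61.
- Any D below 0 then has an upper limit below 1.61, so at this precision the pattern cannot occur.
- It needs an SD above 2/(1.96√(2/74)) = 6.21, or about 2(1.96 × 5/2)² = 48 or fewer per arm.
- Section 3.1 also plans an analysis of treatment completers. With the assumed dropout, 74 × 0.78 ≈ 58 and 74 × 0.55 ≈ 41, the half-width is 1.96 × 5√(1/58 + 1/41) = 2.00, which is borderline.
- If SD 5 belongs to a single score, the change-score SD is 5√(2(1 − r)). It exceeds 6.21 when r is below 1 − (6.21/5)²/2 = 0.23. The documents give no r.

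**The interval level**

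Power at D = 0 is Φ(2/SE − z₁₋α), with 2/0.822 = 2.433.

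- 95% interval (one-sided .025): Φ(2.433 − 1.960) = Φ(0.473) = 0.68.
- 90% interval (one-sided .05): Φ(2.433 − 1.645) = Φ(0.788) = 0.78.

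**The case against.** The formal rule in 3.8d is correct and clear, the Statistical Analysis paragraph repeats the null for each outcome, and Figure 8 only illustrates hypothetical patterns. An analyst who follows the formal rule reaches the right answer. Result 3 may be a one-word slip, since the other three results all conclude about ABC-I. The 95% level appears only in a caption, and the plan never says that its alpha of .05 is one-sided. All of this stands. It limits the point to a conflict between a rule and its illustration.

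A reader might go further and infer that the guide would make a trial favourable to ABC-I be reported as failing to show non-inferiority. The documents do not support that. It requires Result 4 to use a margin of -2, and the text gives only a single positive δ. Against +2, the refusal in Result 4 is right wherever the point estimate lies. The precision calculation makes -2 plausible on the improvement scale, but the patterns need not match the planned precision, and the drawing was not in the copy available for this review.

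The size of that conditional risk is as follows. Against -2, the Result 4 pattern needs D between -3.61 and -0.39. This has probability 32% when the arms are truly equal. It has probability 77% when ABC-I is truly 1 point better, where the formal rule with a 95% interval succeeds with probability Φ((2 − 1.61 + 1)/0.822) = 95%. These figures apply only under the -2 reading and are not consequences of the stated rule.

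**Conclusion.** The point holds as an inconsistency in the decision guide. Result 3 draws a conclusion about CBT-I that no hypothesis covers, and on the improvement scale it fails to credit ABC-I wherever δ is placed. Result 4 is correct with δ at +2 and wrong only with δ at -2; the text leaves this open. The scale is also unstated.

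The 95% interval corresponds to one-sided .025, and the plan does not reconcile it with alpha .05. The choice moves power at N = 148 from about 78% (one-sided .05) to about 68% (one-sided .025). Both are below the stated .80, the first only slightly. These values assume SD 5, truly equal arms and full data.

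This is worth correcting before analysis, but it does not undermine the test itself, because the governing rule in 3.8d is sound.

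**What to change.** In Section 3.8d and Figure 8:

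1. State that the difference is CBT-I minus ABC-I in improvement, and mark +δ only.
2. Replace the four verdicts with one rule: ABC-I is non-inferior if and only if the upper confidence limit is below +δ. This also closes the gap in Result 2.
3. Reword Result 3 to say that non-inferiority of ABC-I is established, and tie Result 4 to the upper limit reaching +δ.
4. State one alpha with its matching interval, either 95% with one-sided .025 or 90% with one-sided .05. Restate power at N = 148 accordingly, about 68% or 78%, with the SD and the assumed true difference given.

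The cost is a correction to text and figure, with no change to conduct or data collection. The consequence to accept is a stated power below .80. By the calculation above, reaching .80 at d = 0.40 would take 156 participants at one-sided .05 or 198 at one-sided .025.

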Table 6 shows the projected number of individuals who are expected to be excluded for the reasons listed above, and the number expected to discontinue participation prior to randomization (5%). We have accounted for this in the derivation of our sample as well. We anticipate that a total of 198 women will be deemed appropriate and will agree to randomization. The required sample size of 148 women is therefore feasible given the projections described here.

Table 6: Estimates of eligibility determination prior to randomization

	Projected N(%)
Number (%) consented and enrolled	400
Excluded: untreated sleep disorders	140 (35%)
Excluded insomnia remission	4 (1%)
Excluded: unstable/severe medical or psychiatric condition discovered during assessment	48 (12%)
Number (%) of consented) eligible for randomization	208 (52%)
Withdraw after baseline, prior to randomization	10 (5%)
Number who agree to be randomized	198 (95%)
Number (%) randomized	148 (75%)

3.4c. Randomization: Individuals who complete the study baseline assessment and meet all inclusion/exclusion criteria will be randomly assigned to one of the two intervention groups: ABC-I (n=74), or CBT-I (n=74). [name] will make all final determinations regarding eligibility for randomization with input from the study physicians. Both interventions are described in detail below. Randomization procedures will follow the CONSORT criteria for randomized trials.⁴⁷ Stratified randomization will be used to help insure that ABC-I and CBT-I groups are balanced in baseline severity of sleep problems. Strata will be based on hours of sleep reported on the screening postal survey (>6 hours vs. \leq 6 hours). The number of subjects in each stratum is not expected to be equal, but within each stratum, half will be assigned to each group (ABC-I and CBT-I). This will help to insure balance in baseline severity across the two treatment groups.

[name] (statistician) will generate the stratified randomization sequence. A set of envelopes containing the group assignment will be generated and the data manager ([name]) will store the randomization envelopes in a secure file drawer that only she and [name] can access. Once eligibility is determined, [name] will open the next envelope in sequence within the appropriate stratum.

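### For Aims 2 and 3 the plan does not fix the error level of the non-inferiority test, and the claimed .80 power is unsupported at either level it could mean

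*Combined protocol and SAP*

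**What the plan says.** All of this is in section 3.8d, Data analysis for Aims 2 and 3.

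- **The test.** Under Description of analysis, H0 is that CBT-I minus ABC-I is at least delta: "This is tested by formulating a one sided null hypothesis". The consequence of rejecting H0 is given as: "hypothesis is rejected, then the non-inferiority of ABC-I is established".
- **The interval rule.** The text on Figure 8 turns this into an interval criterion. For Result 2 it says "the confidence interval excludes δ and the noninferiority of ABC-I is established", and the caption adds "The figure shows mean differences and 95% CI".
- **The sizing.** Under Sample Size Calculations: "The required sample size (with alpha=.05 and .80 power) to detect for an effect size of 0.40 is n=138". This is the only alpha given for Aims 2 and 3, and its sidedness is not stated. The section then concludes that 148 randomized participants give sufficient power.
- **The margin.** Delta is set at d=0.40. "With respect to ISI, this represents a 2 point difference between the treatment effects".

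Nowhere does the plan mention .025, a 90% interval or a one-sided confidence bound, and it does not say how the one-sided test relates to the 95% interval. Section 3.1 makes adherence and attrition the primary outcomes, so the tests affected here are not primary.

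**The concern.** A one-sided test at .05 corresponds to one limit of a two-sided 90% interval excluding delta. Requiring a two-sided 95% interval to exclude delta is a one-sided .025 test. A result with one-sided p between .025 and .05 is therefore non-inferior under one rule and not established under the other, and the text can be cited for either.

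The level applies to each Hypothesis 2 and 3 non-inferiority verdict: ISI, PSQI and actigraphic sleep percent, at post-treatment and at 3 months. It sets the chance of accepting a treatment that is worse by exactly delta (5% or 2.5%), and it sets the power. If the plan leaves it open, nothing prevents the level from being settled once results are known.

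**Working it through.** **Inputs.** Margin d=0.40, alpha .05, power .80 and N=138 (3.8d); 74 per arm (3.4c); ISI margin 2 points (3.8d), so the implied SD is 2/0.40 = 5. Assumed because the plan does not say: true difference zero, complete data, no covariate adjustment, and 0.40 expressed in SDs of the analysed contrast.

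**1. The plan's own 138.** Per arm, n = 2(z_alpha + z_power)²/d².
- One-sided .05: 2(1.645 + 0.842)²/0.16 = 77.3, so 78 per arm, total 156.
- One-sided .025: 2(1.960 + 0.842)²/0.16 = 98.1, so 99 per arm, total 198 (200 with the noncentral t).

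Neither gives 138. Solving for alpha gives z = 0.40·√(138/4) − 0.842 = 1.508, a one-sided level of about .066, which the plan states nowhere. The sample size therefore does not show which level was meant.

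**2. What alpha means elsewhere in the plan (3.8c).**
- Table 11, 22% versus 45%: two-sided .05 with continuity correction gives 148, as printed. All 49 cells reproduce this way.
- Bedtime deviation: (1.960 + 0.842)²·(36² + 19²)/20² = 32.5, so 33 per group, as stated. One-sided .05 would give 26.
- Rise-time deviation: (1.960 + 0.842)²·(40² + 14²)/30² = 15.7, so 16 per group, as stated. One-sided .05 would give 13.

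For Aim 1, an alpha of .05 is thus two-sided.

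**3. Power.** Power = Φ(0.40·√(n/2) − z_alpha), n per arm. At n=74, 0.40·√37 = 2.433.

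| Rule | N=138 | N=148 |
|---|---|---|
| One-sided .05 (90% CI) | 76% | Φ(2.433 − 1.645) = 78% |
| One-sided .025 (95% CI) | 65% | Φ(2.433 − 1.960) = 68% |

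The difference at N=148, about 10 in 100, is the share of trials of an equally effective ABC-I that would receive opposite verdicts.

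**4. On the ISI scale.** SE = 5·√(2/74) = 0.82. Non-inferiority requires an observed CBT-I advantage below
- 2 − 1.655 × 0.822 = 0.64 points at one-sided .05;
- 2 − 1.976 × 0.822 = 0.38 points with the 95% interval.

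An observed 0.5 gives one-sided p = .035. The 90% upper limit is 1.86, which excludes 2. The 95% upper limit is 2.12, which does not.

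**5. Sensitivity to the SD.** The planned tests are change contrasts. If 0.40 is in raw-score SDs, the change-score SD is the raw SD times √(2(1 − ρ)), where ρ is the correlation with baseline. The plan gives no ρ.

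| ρ | Power, one-sided .05 | Power, 95% CI | Opposite verdicts | ISI zone (points) |
|---|---|---|---|---|
| 0.3 | 66% | 54% | 12 per 100 | 0.08 to 0.39 |
| 0.5 | 78% | 68% | 10 per 100 | 0.38 to 0.64 |
| 0.7 | 93% | 88% | 5 per 100 | 0.74 to 0.95 |

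At ρ = 0.5 the change-score SD equals the raw SD, so that row repeats steps 3 and 4.

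**The case against.** The strongest reply is that there need be no contradiction. A one-sided null gives the direction of the test, not its level, and is commonly tested with one limit of a two-sided 95% interval. If .05 is two-sided, as in every Aim 1 calculation, the sizing sentence and the Figure 8 caption agree. This stands. A reader might infer that the plan sizes the test at one-sided .05 and then decides it at .025. The documents do not support that, because the sidedness is never stated and the Aim 1 figures point the other way. But the two-sided reading needs about 198 participants, further from 138 than the 156 of the one-sided reading, so it removes the conflict and widens the power shortfall.

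Three further replies stand only in part:

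- **Figure 8 is illustrative.** Its result patterns are hypothetical, it concerns only the ISI, and the drawing could not be examined. The Statistical Analysis text tests contrasts and mentions no interval. Even so, the text on Figure 8 is the plan's only account of how an interval leads to a verdict.
- **The 95% interval might be a one-sided bound.** That would reconcile it with one-sided .05, but the plan does not say so, and power would still be about 78%.
- **Variance reduction could recover the power.** Baseline adjustment with a correlation of about 0.33 (one-sided .05) or 0.54 (one-sided .025) would give 138. Section 3.8b says only that covariates may be used and gives no correlation. Nor would this settle the level.

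A reader might also infer that the sponsor intends to pick the level after seeing results. Nothing in the plan suggests that.

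**Conclusion.** The error level of the Aim 2 and 3 non-inferiority tests is unspecified, and the power claim does not hold on the plan's own inputs at either candidate level. Under the assumptions listed in the working, power at N=148 is about 68% with the 95% interval and about 78% with one-sided .05. It exceeds .80 only with a variance assumption that the plan does not state: at a baseline correlation of 0.7, for example, the two figures are 88% and 93%.

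It would go too far to say that only the 95% interval rule breaks the power claim, or that adopting one-sided .05 with a 90% interval restores it. Both fall short, and 138 matches neither. It would also go too far to extend this to the primary outcomes: the Aim 1 sizes are consistent with two-sided .05 and are unaffected.

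**What to change.** In section 3.8d, before data are seen, state one level and its matching interval. Either pair is coherent:

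- one-sided .025 with the two-sided 95% interval already named in the Figure 8 caption; or
- one-sided .05 with a two-sided 90% interval, changing the caption to match.

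Define the rule explicitly: non-inferiority is established when the upper limit of the interval for CBT-I minus ABC-I benefit lies below delta, with every outcome scored so that higher is better. The scoring clause is needed because lower ISI and PSQI scores are better while a higher sleep percent is better. Use the same level in the description of the test, the Figure 8 text and caption, and the sample size paragraph.

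Replace the .80 claim with the power at N=148 for the chosen level: about 68% for the first option or about 78% for the second. State whether 0.40 is in raw-score or contrast SDs and what baseline correlation is assumed. If baseline adjustment is relied on for power, specify it.

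The cost is wording, possibly one caption, and a less favourable stated power. No extra patients or data are needed.

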3. RESEARCH DESIGN AND METHODS

3.1. Basic Study Design

The proposed study is a 4-year randomized trial to test the effectiveness of a novel treatment program for insomnia among women Veterans receiving outpatient care. The basic design is shown in **Figure 7**. As in our prior work, we will identify potential participants using a postal screening survey, including questions targeting ICSD diagnostic criteria for insomnia.⁴⁶ This survey will be sent to women who have received outpatient care (at least one visit) at the VA Greater Los Angeles Healthcare System (VAGLAHS) within the prior six months and live within a 50 mile radius of the Sepulveda Ambulatory Care Center (SACC) where the study will be conducted. Those who return the survey indicating symptoms of insomnia will be contacted by telephone to clarify study eligibility and to invite them for in-person screening/enrollment and baseline assessments. We anticipate enrolling a total of 400 women to achieve the proposed sample of 148 randomized participants (74 to receive ABC-I, and 74 to receive CBT-I).

[figure not shown]
Participants will complete a comprehensive sleep, mental health and physical health assessment at baseline (pre-treatment), immediately after the intervention ends (post-treatment), and 3 months after the end of the intervention (3-month follow-up). The primary outcomes will focus on differences in treatment adherence and attrition. We will also compare the effectiveness of the two interventions in terms of improving self-reported sleep quality and insomnia symptoms, plus objectively monitored sleep/wake patterns (wrist actigraphy) measured at post-treatment and at the 3 month follow-up using a non-inferiority design. Data will be analyzed both for treatment completers and for all randomized participants in an intention to treat analysis. Based on our recent work in this area, we expect to be able to enroll and randomize 148 women Veterans into the study within the proposed time frame. The planned research has been informed by our recently-completed HSR&D funded pilot study,⁴⁶ and our ongoing HSR&D funded intervention trial of CBT-I with older Veterans (PI: [name]).

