3.8. Data analysis plan

3.8a. Overview: Below we provide an overview of the study design considerations, and the analysis plan for each aim. We first present the approach for Aim 1, which involves traditional between-groups comparisons. Given the comparative effective approach required by Aims 2 and 3, we discuss these separately, and provide details regarding the structure of hypothesis testing for this method. In particular, we focus on the null hypothesis testing procedure and the determination of the clinically-meaningful effects (i.e., delta or δ) to be considered with respect to non-inferiority.

3.8b. Study Design Considerations: The equivalency of the two treatment groups at baseline is produced by the random assignment to groups. Randomization (combined with the ITT analysis strategy) should produce groups that differ only by chance with respect not only to factors related to study outcomes, and also to the outcomes themselves. Nevertheless, the adequacy of the randomization will be assessed by comparing the groups across outcomes measured at baseline. We will use a stratification based on hours of sleep reported on the postal survey (>6 versus ≤ 6 hours) to assign participants to strata for randomization. We have chosen stratified randomization to further increase the likelihood that the groups will be equivalent at baseline. The inclusion of covariates in such a situation would not be for the purpose of ensuring the comparability of the groups (because that comparability is created via randomization), but covariates may be used to enhance statistical power by reducing error variance.

We anticipate that some participants will not complete the intervention; however, we will continue to collect post-treatment and 3-month follow-up data, regardless of whether they complete the intervention program. Participants will be offered monetary incentives for providing post-treatment and follow-up assessments, regardless of whether they complete the intervention program to which they were assigned. We anticipate this will maximize the completeness of data; however, some data loss is unavoidable. In our recent study of older Veterans, we were able to obtain follow-up data for up to one year in 90% of randomized participants.

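### The Aim 2–3 non-inferiority tests compare raw change scores; naming the baseline value as a covariate costs almost nothing and may add appreciable power

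*Combined protocol and SAP*

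**What the plan says.** Section 3.1 sets the hierarchy: "The primary outcomes will focus on differences in treatment adherence and attrition". The sleep outcomes (ISI, PSQI and actigraphic sleep percent) belong to Aims 2 and 3 and are tested for non-inferiority.

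Section 3.8d states that "we will first use a 2 (group) by 3 (time) mixed model analysis of variance (ANOVA", and places baseline, post-treatment and follow-up together in the within-subject factor. For Hypothesis 2, "a planned interaction comparison will be tested that crosses treatment group (ABC-I vs. CBT-I) with time", weighting baseline against post-treatment. The main Hypothesis 3 contrast is obtained by "applying a -1 0 1 contrast to time and interacting that with treatment group". No covariate appears in either description, and neither does the sleep-hours stratum used for randomisation (section 3.4c).

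Section 3.8b says that "covariates may be used to enhance statistical power by reducing error variance", but names none and commits to none.

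On the margin, the sample size text of section 3.8d describes 0.40 as "4/10s of a standard deviation for each outcome measure" without saying whether the SD is that of baseline, follow-up or change. The null is one-sided and alpha is 0.05. The caption of Figure 8, which illustrates how non-inferiority is judged, adds: "The figure shows mean differences and 95% CI".

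**The concern.** With baseline as a level of the time factor, the group-by-time contrasts for Hypothesis 2 and the main part of Hypothesis 3 are differences between arms in mean raw change. Subtracting baseline gives it a fixed coefficient of one, whatever its actual relation to the later value. If that relation is weak, subtraction adds noise.

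Non-inferiority depends on the width of the interval against the margin, so avoidable noise bears directly on whether the conclusion can be reached. The plan claims enough power at 148 participants, but without the correlation, the SD ratio or the SD behind 0.40, that claim cannot be confirmed for a change contrast. A general permission to use covariates also leaves it possible to choose them after the data are seen.

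**Working it through.** **The plan's own figure.** Section 3.8d gives a total of 138 for an effect of 0.40, alpha 0.05 and power 0.80. The usual formula with a true difference of zero is n per arm = 2(z₁₋α + z₀.₈)²/0.40².
- One-sided 0.05: 77.3, so 78 per arm and 156 in total.
- One-sided 0.025: 98.1, so 99 per arm and 198 in total.

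The figure of 138 is not reproduced. At the planned 148 the same calculation gives 78.5% or 68.2% power. It uses a per-participant SD of one, so it describes the planned contrast only if 0.40 is in change SDs, or if the SDs are equal and the correlation is 0.5.

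**Inputs.** From the documents: 74 per arm, margin 0.40 SD, one-sided alpha 0.05 (or 0.025 if the two-sided 95% interval decides), and an ISI margin of 2 points, which implies SD = 2/0.40 = 5. Assumed: ρ, the baseline/follow-up correlation, and k, the baseline SD divided by the follow-up SD. The true difference is taken as zero.

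**Variances** (follow-up SD = 1):
- Raw change: 1 + k² − 2kρ
- Baseline-adjusted: 1 − ρ²
- Gap: k² − 2kρ + ρ² = (k − ρ)², which is never negative

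Under randomisation both estimate the same mean difference, so a margin in points carries over unchanged.

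**One cell by hand (k = 1, ρ = 0.3).** The change variance is 1.40, so SE = √(2 × 1.40/74) = 0.195 and 0.40/SE = 2.06. The adjusted variance is 0.91, so SE = √(2 × 0.91/74) = 0.157 and 0.40/SE = 2.55. The noncentral t (146 and 145 df) at one-sided 0.05 gives 65.6% and 81.4%. A comparison of follow-up values that ignores baseline has 78.1%, so here subtracting baseline is worse than not using it.

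**Power (%), planned → adjusted:**

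| Setting | ρ = 0.3 | ρ = 0.5 | ρ = 0.7 |
|---|---|---|---|
| 74/arm, k = 1, one-sided 0.05 | 66 → 81 | 78 → 88 | 93 → 96 |
| 74/arm, k = 1, 95% CI rule | 53 → 72 | 68 → 80 | 88 → 92 |
| 74/arm, k = 0.8, one-sided 0.05 | 73 → 81 | 84 → 88 | 96 → 96 |
| 74/arm, k = 0.8, 95% CI rule | 61 → 72 | 75 → 80 | 92 → 92 |
| 74/arm, k = 0.8, 0.40 in baseline SDs, one-sided 0.05 | 56 → 65 | 68 → 72 | 85 → 86 |
| 74/arm, k = 1, 0.40 in change SDs, one-sided 0.05 | 78 → 91 | 78 → 88 | 78 → 84 |
| 74/arm, k = 0.8, 0.40 in change SDs, one-sided 0.05 | 78 → 86 | 78 → 82 | 78 → 79 |
| 67/arm, k = 1, one-sided 0.05 | 62 → 78 | 74 → 84 | 91 → 94 |
| 67/arm, k = 0.8, one-sided 0.05 | 69 → 78 | 81 → 84 | 94 → 94 |

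Unless the row says otherwise, 0.40 is in follow-up SDs. The 67 per arm is a rough 10% loss, taken from section 3.8b, which says of an earlier study that "we were able to obtain follow-up data for up to one year in 90% of randomized participants".

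**Where the gain vanishes.** At k = 0.6 and ρ = 0.5, one-sided 0.05, power goes from 87.1% to 87.5%. The only correlation over time given for one of these outcomes is the PSQI one-month retest value of 0.85 (section 3.5d). It is not a correlation across treatment; at k = 1 it would give 99.7% → 99.8%.

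**Correlation needed for 80% power (one-sided 0.05), planned vs adjusted:** 0.53 vs 0.23 (74 per arm, k = 1); 0.57 vs 0.38 (67 per arm, k = 1); 0.65 vs 0.63 (74 per arm, k = 0.8, margin in baseline SDs).

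**ISI 95% half-width** = t₀.₉₇₅ × 5 × √(2 × variance/n), against the 2-point margin, for ρ = 0.3/0.5/0.7:
- 74 per arm, k = 1: 1.92 → 1.55, 1.62 → 1.41, 1.26 → 1.16
- 74 per arm, k = 0.8: 1.75 → 1.55, 1.49 → 1.41, 1.17 → 1.16
- 67 per arm, k = 1, ρ = 0.3 only: 2.02 → 1.63

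**Simulation check** (10,000 runs per cell, one follow-up time). With the true difference set at the margin, rejection at nominal 0.05 was 0.047–0.054 for change and 0.045–0.054 for adjusted. Both tests hold their level.

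**The case against.** The planned contrasts are valid, clearly written and match the wording of Hypotheses 2 and 3, which speak of improvement from baseline. The outcomes are not primary, and section 3.8b already recognises that covariates can add power. All of this is correct: the change is an improvement, not the repair of an error.

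The size is also open to challenge. Neither ρ nor k is in the documents. An 18-point gain needs ρ = 0.3, k = 1 and the 95% interval rule together; at one-sided 0.05 the same cell gives about 16. Nor is 18 a ceiling, since ρ = 0.2 gives about 21. Enrolment requires insomnia, which could narrow the baseline spread and push k below one. If 0.40 is in change SDs, planned power is 78% at any correlation, close to the stated 80%. For PSQI, section 3.8d also gives margins of 1.8 and 2 points besides 1.4. With the SD of 3.5 implied by 1.4 points (1.4/0.40), k = 1, ρ = 0.3 and one-sided 0.05, planned power is then already 84% or 90%. With 74 per arm, every ISI half-width shown is below 2.

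These points limit how much may be gained. They do not favour the change contrast: adjustment still helps under the change-SD reading and under the wider PSQI margins (84% → 95% and 90% → 98%). A general permission that names no covariate is not pre-specification. The plan's multiple imputation is no obstacle, because the adjusted model can be fitted to each imputed data set.

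**Conclusion.** The point holds, as an efficiency and pre-specification matter confined to Aims 2 and 3. The tests of Hypothesis 2 and the main Hypothesis 3 contrast use raw change, and no baseline covariate is committed to. Baseline adjustment targets the same difference and the same margin, and its variance is smaller by (k − ρ)². The gain runs from about 0 to 18 percentage points of power over the settings tabulated (ρ 0.3 to 0.7, k 0.6 to 1, true difference zero). It is largest when the correlation is low and the SDs are similar. Because ρ, k and the SD behind 0.40 are all unstated, the plan does not show that its contrast has 80% power at 148. No bias is alleged. The secondary contrast between post-treatment and 3 months does not use baseline and is unaffected, as are the Aim 1 tests.

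**What to change.** For ISI, PSQI and sleep percent, pre-specify one longitudinal model of the post-treatment and 3-month values. It should contain group, time, group-by-time, the baseline value of that outcome by time, and the sleep-hours randomisation stratum, with unstructured covariance. The stratum is there to match the design; its effect on power is negligible. Compare the adjusted group difference at each time with the margin, fitting the model to the imputed data sets where imputation is used. Keep the planned change contrasts as sensitivity analyses. State the assumed baseline-to-follow-up correlation and whether 0.40 refers to the baseline, follow-up or change SD.

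The cost is wording in the analysis plan and about one degree of freedom per covariate. The baseline measures are already collected, and no extra participants or visits are needed.
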